7.4.5.2 Evaluation

The time scale considered will be the month.

Survival rates will be calculated at different time points using the Kaplan Meier estimator and its 95% confidence interval.

7.4.6 Progression-free survival

Population: ITT

7.4.6.1 Definition of progression-free survival

It is defined as the time interval between the date of inclusion and the date of 1^{ère} radiological progression or the date of death (from any cause). Patients alive and without progression will be censored at the date of last news.

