- If the following grade 3 or 4 toxicities occur as a result of chemoembolization, no additional session will be performed (but FOLFOX will be continued).

- Arteritis
- Grade 3 or 4 hepatic impairment
- Local ischemic and septic manifestations (cholecystitis, hepatic infarction, hepatic abscess, digestive hemorrhage) of grade 3 or 4
- Grade 3 or 4 renal insufficiency
- **The interval between chemoembolization sessions may be extended to allow for recovery of liver function.**
- No dose adjustment of irinotecan is planned for chemoembolization sessions.
- In case of hematological toxicity, FOLFOX dose adjustment rules **will be applied and chemoembolization will be continued.**

In case of doubt, do not hesitate to ask for advice from the study's referring radiologist, [name], through the FFCD.

VII. PATIENT MONITORING DURING TREATMENT AND AFTER WITHDRAWAL OF TREATMENT

Monitoring during treatment:

- **Before each cycle of FOLFOX:**
 - Complete clinical examination including: weight, vital signs, WHO, pain assessment (VAS)
 - Biological check-up: CBC/platelets
 - Adverse event evaluations according to NCI CTC version 4.0
- **Before each chemoembolization session**
 - Complete clinical examination including: weight, vital signs, WHO, pain assessment (VAS)
 - Biological workup consisting of measurements of hematological, nephrological and hepatic parameters: CBC/platelets, blood ionogram, creatinine, albumin, transaminases (AST, ALT), alkaline phosphatases (ALP), total and conjugated bilirubin, PT
 - Adverse event evaluations according to NCI CTC version 4.0

CEA and CA 19-9 assays, as well as thoracoabdomino-pelvic CT and liver MRI will be performed at an initial evaluation between D63 and D70 and then every 2 months after the start of treatment.

For patients participating in the associated 'lipid' translational study, please remember to perform the fasting sample and then technician the sample.

After the chemoembolization treatment period:

All patients will receive chemotherapy with FOLFOX every 2 weeks according to the usual regimen until progression or unacceptable toxicity.

VIII. STOP PROCESSING THE STUDY

The processing of the study will be stopped in case of:

- Investigator's decision
- Major toxicity requiring discontinuation of treatment (despite protocol adaptations)
- Serious or unexpected event requiring discontinuation of protocol treatment
- Progression of the disease
- Patient refusal or withdrawal of consent

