The primary endpoint will be the proportion of patients alive without progression (death will be considered as progression) at 9 months after the start of treatment according to RECIST V1.1 criteria, as assessed by the investigator.

Progression-free survival time will be defined as the time interval between the date of inclusion and the date of progression or death (regardless of cause). For patients alive without progression, the time interval between the date of inclusion and the date of last morphological evaluation will be taken.

XII.2.2 Secondary Criteria

The secondary endpoints will be:

- Tolerance to the treatment
- Response rate according to RECIST v1.1 criteria at 9 months (according to the investigator)
- Response rate according to EASL criteria (assessed by centralized review) at 9 months
- Hepatic progression-free survival according to RECIST v1.1 criteria at 9 months
- Overall survival
- Progression-free survival
- The rate of secondary resections
- Changes in tumor marker levels

Liver progression-free survival will be defined as the time interval between the date of inclusion and the date of liver progression as assessed by the investigator's RECIST V1.1 criteria or death (regardless of cause) or the date of the last morphological assessment for patients alive without progression.

Overall survival will be defined as the time interval between the date of inclusion and the date of death regardless of the cause of death or the date of last news for living patients.

Tolerance to treatment will be assessed by:

- duration of treatment, doses received, dose reductions and deferrals
- Toxicities collected at each monthly visit, and described according to NCI-CTC version 4.0 criteria; Grade 3, Grade 4 and Grade 5 toxicities will be reviewed
- the number and description of SAEs

Changes in tumor marker levels (CEA and CA 19-9) will be assessed throughout the study.

XII.3 Calculation of the number of subjects needed

A 1-step Fleming design will be used, with a one-sided α risk of 5% and a power (1- β) of 90%.

The assumptions are:

- H0: A proportion of patients living without progression of 55% during the first 9 months is uninteresting;
- H1: A proportion of patients living without progression of more than 55% during the first 9 months would show the interest of the treatment; a proportion of 75% is hoped for.

Total number: **48 evaluable patients**

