6.2 Agreements concerning dates and durations

Time since inclusion will be defined as the time since the day of inclusion, with the day of inclusion considered day 1. Therefore, the durations will be calculated according to the following rule, for example for the duration between death and inclusion: day of death - day of inclusion **+ 1**.

The day before the day of inclusion (resp. the day before the day of treatment) will be considered as day -1 (day 0 does not exist).

The last date of news will be the date of the last examination performed or the last treatment or the last medical consultation/visit.

The following conversion rules will be used to convert the number of days into months or years: 1 month = 30.4375 days; 1 year = 365.25 days.

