7.4.7.1 Definition of overall survival

It is defined as the time interval between the date of inclusion and the date of death (regardless of cause).

Patients lost to follow-up or alive at the time of analysis will be censored at the date of last report.

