7.6 Exploratory Analyses

7.6.1 Definition

The exploratory analysis focuses on the search for factors predictive of progression-free survival and/or overall survival.

Progression-free survival is defined as the time interval from the date of inclusion to the date of 1^{ère} radiological progression or the date of death (from any cause). Patients alive and progression-free will be censored at the date of last report.

Overall survival is defined as the time interval between the date of inclusion and the date of death (regardless of cause). Patients lost to follow-up or alive at the time of analysis will be censored at the date of last report.

The variables for which the p-value is lower than 0.10 in univariate analysis or judged clinically relevant among the list to be defined will be retained for the multivariate analysis.

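### The SAP censors secondary PFS and hepatic PFS at last news, the protocol at the last morphological evaluation; the SAP curves can only be equal or higher

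*SAP*

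**What the plan says.** The protocol uses two different end dates. For PFS time in patients alive without progression, XII.2.1 states that "the time interval between the date of inclusion and the date of last morphological evaluation will be taken". For hepatic PFS, XII.2.2 uses "the date of the last morphological assessment for patients alive without progression". Only overall survival runs to last contact: "the date of death regardless of the cause of death or the date of last news for living patients".

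The SAP moves both PFS endpoints to the overall-survival date. SAP 7.4.6.1 (PFS) and 7.4.5.1 (hepatic PFS) each state: "Patients alive and without progression will be censored at the date of last news". The PFS definition for the exploratory models in SAP 7.6.1 reads: "Patients alive and progression-free will be censored at the date of last report". Last report appears to be the same date as last news, because SAP 7.4.7.1 uses it for overall survival ("Patients lost to follow-up or alive at the time of analysis will be censored at the date of last report") where the protocol says last news.

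SAP 6.2 defines the date: "The last date of news will be the date of the last examination performed or the last treatment or the last medical consultation/visit". It therefore need not be a scan. The SAP gives no reason for departing from the protocol.

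**The concern.** Progression is radiological in the SAP definitions, so it cannot be recorded after the last scan. Censoring at last news nevertheless keeps the patient in the denominator, event-free, until the last contact.

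A gap between the two dates is plausible here. FOLFOX is given every 2 weeks, while imaging is "performed at an initial evaluation between D63 and D70 and then every 2 months after the start of treatment" (Protocol VII). Protocol VIII allows treatment to stop without progression (toxicity, refusal, investigator's decision), and these patients stay in the intention-to-treat and overall survival analyses. The scan schedule appears under monitoring during treatment, and no separate schedule after treatment is given. SAP 7.3.1 itself provides for patients without a 9-month scan.

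At stake are the median PFS, the PFS rates at 6, 9, 12 and 18 months, and hepatic PFS. Each would have two values depending on which document is followed, and the unexplained choice is the one that cannot be less favourable. The PFS times in the exploratory Cox models also change, but no direction can be claimed for the hazard ratios.

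**Working it through.** **1. The primary endpoint uses no censoring date.** The one-step design reproduces by the normal approximation with p0 = 0.55, p1 = 0.75, one-sided 5% and 90% power: n = [(1.645·√(0.55·0.45) + 1.282·√(0.75·0.25)) / 0.20]² = 47.1, planned as 48. The cut-off is 48·0.55 + 1.645·√(48·0.55·0.45) = 32.07, so 33 successes. The analysis is a count of patients classified from scans, with its own window and missing-scan rules (SAP 7.3.1) and an exact interval (SAP 7.3.2). The censoring rule does not enter, and 33 of 48 stands.

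**2. Direction.** The Kaplan-Meier estimate is S(t) = Π(1 − dᵢ/nᵢ) over event times up to t. Both rules count the same progressions and deaths on the same dates, so every dᵢ is unchanged. Later censoring can only keep or enlarge each nᵢ. Each factor, and hence S(t), is therefore equal or higher under the SAP rule. There were no violations in 5,000 random datasets.

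**3. Size for overall PFS.** The documents do not give the gap between last scan and last news, so the figures below are illustrations and not bounds. Assumptions:
- Total hazard −ln(0.55)/9 per month, with 10% or 30% of it death without progression.
- Median survival after progression 6, 12 or 18 months.
- Progression dated at the next scan (2.2, 4, 6, 8… months).
- 20% of patients have no scan after month 4 or 6 if still event-free, then stay in contact for C months.
- Cut-off at 27 months; 200,000 patients per scenario.
- Deaths known only while in contact (A), or known to the cut-off (B).

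SAP rule minus protocol rule, in percentage points:

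| C (months) | A, 9 months | A, 18 months | B, 9 months | B, 18 months |
|---|---|---|---|---|
| 1 | 0.10–0.31 | 0.05–0.16 | 0.05–0.15 | 0.02–0.08 |
| 3 | 1.74–1.95 | 0.90–1.03 | 0.66–1.15 | 0.34–0.60 |
| 6 | 1.65–3.52 | 2.64–2.84 | 0.75–2.23 | 0.99–1.90 |
| 12 | 1.25–3.06 | 4.97–6.31 | 0.75–2.23 | 2.60–4.88 |

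If patients leave imaging at month 10 or 12, the difference is 0.00 at 9 months. At 18 months it is 0.04–0.17 (C = 1) or 0.49–1.05 (C = 3). If nobody leaves imaging, it is 0.00 with one common cut-off. With follow-up spread over 9–45 months it is 0.01–0.04 at 9 months and 0.07–0.21 at 18 months.

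**4. Trial size.** With 58 patients, of whom on average 58 − 48 = 10 leave imaging at month 4 or 6 with 3 months of further contact, the mean difference is +0.8 to +1.5 points at 9 months and +0.4 to +0.8 at 18 months. The 95% confidence interval half-width at 9 months is 12.8–13.2 points. In 10,000 simulated trials the SAP estimate was never below the protocol estimate at 6, 9, 12 or 18 months.

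**5. A second, simpler model.** It has 58 patients, exponential PFS, scans every 2 months, no deaths before progression, imaging stopped at a random time in months 2–18, and a mean gap to last news of 1 to 12 months. Ranges cover 9-month PFS rates of 55% and 75%.

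| Share leaving imaging | Shift at 9 months | Shift at 18 months |
|---|---|---|
| 10% | 0.1–0.6 | 0.2–1.7 |
| 20% | 0.2–1.1 | 0.4–3.5 |
| 40% | 0.4–2.3 | 0.9–7.7 |

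**The case against.** The conflict in the text is not in dispute. The case against concerns how much it matters and which rule is better.

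- **Small and descriptive.** These are secondary curves in a single-arm trial with no test, and a shift of 1 to 2 points is well inside a half-width of 13. This stands, and it limits the weight of the point. It does not explain why two governing documents should give two values.
- **The 20% is borrowed.** The planning allowance covers patients lost to follow-up or not evaluable, which is not the same group as patients who are still seen but no longer scanned. This stands; 20% is an assumption.
- **The main model uses the 55% rate.** At the hoped-for 75%, with 3 months of contact, a run of the same model gave about +1.1 points (A) or +0.8 (B) at 9 months, against +1.8 or +0.9 to +1.0 at 55%. This stands.
- **The protocol rule is not always nearer the truth.** At 55%, coding A, 3 months of contact, the 9-month values were 57.9% (protocol), 59.7% (SAP) and 58.3% with everyone scanned to progression. So 0.4 of the 1.8 points is protocol underestimation. With 12 months of contact, coding A, the 18-month values were 27.8–29.1%, 32.8–35.4% and 30.2–30.3%. In one 75% scenario at 18 months the SAP rule was closer (55.2%, 55.8%, 56.2%). In nearly all cases run, the protocol rule was closer.
- **Hepatic PFS was not simulated.** Its shift could be larger if patients with extrahepatic progression only are followed without liver imaging. Neither document clearly fixes an end date for them, so the direction is not established for that group.
- **The direction needs a reading of SAP 6.2.** It assumes the latest of the listed contacts is meant and that imaging counts as an examination. That is the natural reading.
- **The primary endpoint rules have a gap.** SAP 7.3.1 does not classify a living, evaluable patient whose last scan precedes the window and who has no later scan. That is a separate question and does not involve the PFS censoring date.

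**Conclusion.** The concern holds. The SAP replaces the protocol's censoring date for PFS and hepatic PFS with a later or equal one, without giving a reason, and the resulting Kaplan-Meier estimates can only be equal or higher for patients alive without any progression. The amount is unknown. For overall PFS it is near zero if contact stays within one 2-month scan interval. It is zero to about 2 points if 20% leave imaging and are seen for up to 3 more months. It is larger only with early exit and long contact: up to 3.5 points at 9 months (6 months of contact) and 6.3 points at 18 months (12 months of contact), part of which is the protocol rule falling below the true value. That it is probably small is a judgement, and it has not been shown for hepatic PFS. The 9-month Kaplan-Meier rate in SAP 7.4.6.2 is affected; the binary 9-month primary endpoint and its decision rule are not. This should be corrected, but it does not threaten the trial's main conclusion.

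**What to change.** In SAP 7.4.5.1, 7.4.6.1 and the PFS definition of 7.6.1, censor patients alive without progression at the date of the last morphological evaluation, as in Protocol XII.2. Keep last news for overall survival, and use it for PFS only as a labelled sensitivity analysis. If the sponsor prefers last news for PFS, justify the change before database freeze and report both estimates.

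An optional clarification, since both documents share the wording: define hepatic PFS censoring for patients alive without *hepatic* progression, at the last morphological evaluation.

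The cost is a few words in three definitions. Scan dates are already collected. The downside is that the reported secondary PFS figures may be slightly less favourable.

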7.4.6.2 Assessment of progression-free survival

The time scale considered will be the month.

Progression-free survival will be plotted using the Kaplan Meier estimator and survival rates at different time points (6, 9, 12 and 18 months) will be calculated along with their 95% confidence intervals.

7.4.7 Overall survival

Population: ITT

7.4.7.1 Definition of overall survival

It is defined as the time interval between the date of inclusion and the date of death (regardless of cause).

Patients lost to follow-up or alive at the time of analysis will be censored at the date of last report.

7.4.7.2 Evaluation of overall survival

The time scale considered will be the month.

Overall survival will be plotted using the Kaplan Meier estimator and survival rates at different time points (6, 9, 12 and 18 months) will be calculated along with their 95% confidence intervals.

7.4.8 Secondary resection rate

Population:

7.4.8.1 Definition

The secondary resection rate is defined as the percentage of patients who had surgery for liver metastases.

The calculated secondary resection rate is defined as the percentage of R0 resection, R1 resection and R2 resection.

7.4.8.2 Evaluation

Rates will be described using standard descriptive statistics.

7.4.9 Evolution of tumor marker levels

7.4.9.1 Definition

The evolution of tumor markers (CEA and CA19-9) will be evaluated throughout the study, from inclusion to progression. It will be described at each evaluation.

7.4.9.2 Evaluation

The delta for CEA and CA19-9 (value at assessment - value at baseline/value at baseline) *100 will be described at each assessment and plotted as a boxplot.

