6.4 Definition of the baseline

Baseline measurements will be the last measurement taken prior to inclusion or the last measurement taken prior to the first administration of treatment.

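### The SAP's only formula for change in CEA and CA 19-9 lacks its inner parentheses and, taken literally, does not depend on baseline (wrong as written, minor)

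*SAP*

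**What the plan says.** Protocol XII.2.2 lists tumour-marker change among the secondary criteria and says only this about it: "Changes in tumor marker levels (CEA and CA 19-9) will be assessed throughout the study". It gives no formula.

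SAP 7.4.9.1 sets the period: "The evolution of tumor markers (CEA and CA19-9) will be evaluated throughout the study, from inclusion to progression". SAP 7.4.9.2 then supplies the calculation. It names the quantity "The delta for CEA and CA19-9" and defines it, inside one outer pair of parentheses, as "value at assessment - value at baseline/value at baseline) *100". The result "will be described at each assessment and plotted as a boxplot".

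Baseline is defined in SAP 6.4: "Baseline measurements will be the last measurement taken prior to inclusion or the last measurement taken prior to the first administration of treatment". Units are in SAP 7.1.4: µg/L for CEA (listed there as ACE) and U/mL for CA 19-9. Neither document gives another expression for marker change, or any test, threshold or decision rule that uses it.

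**The concern.** A percent change needs the difference from baseline in the numerator and baseline in the denominator. The printed expression has only an outer pair of parentheses, and the slash joins only the two baseline terms. Standard precedence, which statistical software follows, divides first. Baseline cancels, and what remains is the current level minus one, multiplied by 100.

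At stake are the marker tables and the boxplots at each assessment. If the formula were coded as printed, they would show the current marker level, shifted and rescaled, under the name of a change. The figures would depend on the unit of measurement, as a percentage does not, and could have the wrong sign. A programmer who silently corrects the formula gets the right answer but departs from the written plan.

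**Working it through.** **Inputs.** V is the value at assessment and B the value at baseline (SAP 7.4.9.2, with B as in SAP 6.4). The documents contain no marker values, so every pair (B, V) below is an assumption chosen to span high and low levels. The plan states no numerical result here, so there is no figure to reproduce.

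**Step 1: the formula as printed.** (V − B/B) × 100 = (V − 1) × 100. B has dropped out.

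**Step 2: percent change from baseline.** 100 × (V − B) / B.

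**Step 3: the gap between them.** Printed minus intended = 100 × (V − 1) − 100 × (V/B − 1) = 100 × V × (1 − 1/B). For positive V the two agree only when B = 1. For B above 1 the printed figure is too high; for B below 1 it is too low.

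**Step 4: numbers.**

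| B | V | Printed: (V − 1) × 100 | Intended: 100 × (V − B)/B |
|---|---|---|---|
| 50 | 10 | (10 − 1) × 100 = +900 | 100 × (−40)/50 = −80% |
| 100 | 50 | (50 − 1) × 100 = +4900 | 100 × (−50)/100 = −50% |
| 100 | 100 | (100 − 1) × 100 = +9900 | 0% |
| 5 | 1.5 | (1.5 − 1) × 100 = +50 | 100 × (−3.5)/5 = −70% |
| 5 | 1 | (1 − 1) × 100 = 0 | 100 × (−4)/5 = −80% |
| 3 | 0.8 | (0.8 − 1) × 100 = −20 | 100 × (−2.2)/3 = −73.3% |
| 0.5 | 0.8 | (0.8 − 1) × 100 = −20 | 100 × 0.3/0.5 = +60% |

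Check of step 3 on the first row: 100 × 10 × (1 − 1/50) = 980, and 900 − (−80) = 980.

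**Step 5: when the sign is wrong.** The printed result is positive exactly when V is above 1 unit. A fall therefore shows as a rise if V is above 1: by more than 100 if V is above 2, and by less than 100 if V is between 1 and 2. At V = 1 the result is 0. Below 1 a fall keeps its negative sign but has the wrong size, and a rise that stays below 1 shows as a fall (last row).

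**Step 6: what was meant.** The quantity is called a delta, refers to baseline twice, contains a division by baseline and is multiplied by 100. SAP 7.4.3.1 (depth of response) and SAP 7.4.4.1 (early tumour shrinkage) both express change as a relative difference from inclusion. Percent change from baseline is the only sensible reading.

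**The case against.** The strongest reply is that nobody would compute this literally. An author does not write baseline over baseline as a way of writing 1, the intent is plain, and the sponsor's own centre runs the analysis. An unchanged marker of 100 shown as +9900 would be noticed at once. This stands, and it is the main reason the point is minor. It does not make the printed formula correct.

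A second reply is that the bracket may have been lost in translation or in reading the PDF. The SAP is visibly a translation, with French text left in section 4.2, and a stacked fraction flattened onto one line would produce this string. That cannot be excluded. Nothing in the text shows it, however: the expression is an unbroken run with a closed outer pair of parentheses and an explicit slash, and the formulas in SAP 7.5.2.1 and 7.5.2.2 came through legibly. The source file will settle it.

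A reader might also infer more than the documents support:

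- **That every falling marker would show as a large increase.** This fails for values at or below 1 unit, and between 1 and 2 the false rise is under 100.
- **That nearly all patients with a falling marker would be affected.** This needs the distribution of on-treatment values, which the documents do not give.
- **That the compliance formula in SAP 7.5.2.2 shows the authors bracket correctly elsewhere.** It is a simple ratio with no subtraction, so it says nothing about how they bracket a difference over a baseline.

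**Conclusion.** Wrong as written, minor. By the usual order of operations, the only formula for this secondary endpoint returns (value − 1) × 100 and carries no information about change from baseline. That result is pure algebra and needs no assumption about the data. The sizes shown rest on assumed marker values, and how many patients would be affected cannot be determined from the documents.

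Results would be wrong only if the expression were programmed literally, and the documents give no reason to think it was. It would also go too far to infer that the trial's conclusion is at risk: marker change is purely descriptive, and the primary endpoint, sample size and decision rule do not use it.

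**What to change.** In SAP 7.4.9.2, replace the expression with:

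100 × (value at assessment − value at baseline) / value at baseline

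Applied to the assumed pairs above, it gives −80% for 50 to 10, 0% for an unchanged 100, and −70% for 5 to 1.5. First check the source-language file, in case the parentheses or a stacked fraction are intact there. Make the correction before database freeze, the limit that SAP 4.5 sets for changes to the plan, and confirm that the marker program uses the corrected form. The cost is one line of SAP text. No data collection, table layout or other analysis changes, and there is no downside.
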